### 3.2.19 Completer cohorts

A completer cohort will be defined as the subset of study participants in the Full Analysis Set (FAS) that were enrolled and treated with LCM for a specified duration of time. For example, a 6-month completer cohort consists of study participants enrolled and treated with LCM for at least 6 months where a month is defined as 28 days.

Study participants will be classified as belonging to one of the following completer cohorts for the purpose of subgroup analyses:

- 6 months
- 12 months
- 18 months
- 24 months
- 30 months
- 36 months
- 42 months
- 48 months

### 3.2.20 Number and percentage of seizure-free days

The number of seizure-free days will be the total number of days within an interval for which daily diary data was available and no seizures were reported. The percentage of seizure-free days will be computed as 100 times the number of seizure-free days in the interval divided by the number of days in the interval for which daily diary data was available. Days without the corresponding daily diary data will not be used in these computations (ie, days where “not done” is marked on the Seizure Frequency CRF/eCRF module). The change in percentage of seizure-free days will be calculated relative to Baseline (using the Baseline definition in Section 3.3).

### 3.2.21 Seizure time intervals

Study participants will be classified as belonging to one of the following time intervals for the purpose of seizure efficacy analyses:

- $\leq 3$  months
- $> 3$  to  $\leq 6$  months

- >6 to ≤12 months
- >12 to ≤18 months
- >18 to ≤24 months
- >24 to ≤30 months
- >30 to ≤36 months
- >36 to ≤42 months
- >42 to ≤48 months
- >48 months

### 3.2.22 Pediatric Quality of Life Inventory (PedsQL)

The PedsQL is a validated instrument that consists of generic core scales suitable for use with pediatric populations, including those with acute or chronic health conditions. Self-report is measured for pediatric subjects ≥5 years to ≤18 years of age, and parent proxy report of child health-related quality of life (HRQoL) is measured for pediatric subjects ≥1 month to ≤18 years of age. The PedsQL Measurement Model consists of developmentally appropriate forms for pediatric study participants ≥1 month to ≤12 months, ≥13 months to ≤24 months, >2 years to ≤4 years, ≥5 years to ≤7 years, ≥8 years to ≤12 years, and ≥13 years to ≤18 years of age. For each subject, the same version that is used at Baseline should be used for 12 months and thereafter the appropriate age versions should be used.

For versions intended for subjects ≤24 months of age, PedsQL infant scale scores will be calculated for each of the following 5 PedsQL scales:

- Physical Functioning
- Physical Symptoms
- Emotional Functioning
- Social Functioning
- Cognitive Functioning

For versions intended for subjects >2 years of age, PedsQL generic core scale scores will be calculated for each of the following 4 PedsQL scales:

- Physical Functioning
- Emotional Functioning
- Social Functioning
- School Functioning

For versions intended for subjects >8 years of age, Physical Functioning refers to questions “About my health and activities”; Emotional Functioning refers to questions “About my feelings”; Social Functioning refers to questions “How I get along with others”; School Functioning refers to questions “About school”.

The PedsQL assessment is retrospective to the prior one month, and individual items are scored using a 5-point Likert scale (0 to 4 representing responses of: never, almost never, sometimes, often, or almost always). These scores of 0 to 4 will be transformed by the following formula in order to generate scores of 0, 25, 50, 75, and 100 where a higher value represents a better health-related quality of life (HRQoL):

Item transformed score =  $100 - (\text{item raw score} \times 25)$

Each PedsQL scale or dimension score is then calculated as the mean of the transformed item scores from items of the considered dimension. In the case of item-level missing data, these will be replaced by the average of non-missing item scores from the considered dimension, if at least 50% of the items from that dimension are non-missing.

The above algorithm will also be used to calculate the PedsQL total score (all items), the psychosocial health summary score (a combination of the emotional, social and cognitive functioning items), and the physical health summary score (a combination of the physical functioning and physical symptoms items) for each subject  $\leq 24$  months of age. Also, the PedsQL total score (all items), the psychosocial health summary score (a combination of the emotional, social and school functioning items) and the physical health summary score (the physical functioning items) will be calculated for each subject  $> 2$  years of age. These summary scores will be missing if any of the scale scores contributing to their calculation is missing.

### **3.2.23 Hospital stay duration**

The duration of each hospital stay will be calculated as the discharge date minus the admission date (Hospitalization/Emergency Room [ER] Visit Date on the CRF/eCRF module) plus 1 day for hospital stays with a discharge date.

### **3.3 Definition of Baseline values**

In general, Baseline will be defined as the last non-missing value collected prior to the first dose of LCM in the original study for rollover subjects and in SP848 for direct enrollers for safety and efficacy variables unless otherwise noted for a specific type of data. The Baseline value for seizure counts for directly enrolled study participants will be taken from the Historical Seizure Count CRF/eCRF module collected in SP848 in combination with the seizure diary data collected from the date of the Screening Visit to the day prior to the date of first dose of LCM.

For participants enrolling from EP0060 the baselines for the questionnaires will consider each EP0060 enrollment group separately, those are: ILL (Initiating intravenous lacosamide Group: not currently receiving LCM, i.e. LCM naïve), OLL (Open-label lacosamide Group: currently receiving oral LCM in open-label long term study), and RxL (Prescription lacosamide Group: currently receiving prescribed oral LCM from commercial supply, VIMPAT). For ILL group baseline will be Visit 1 from SP848, for OLL group baseline will come from SP848 using above baseline definition, and for RxL group there will be no baseline data as they were on oral LCM prior to EP0060.

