## **3.2 General study level definitions**

### **3.2.1 Analysis time points**

#### **3.2.1.1 First and last dose of LCM**

Unless otherwise noted, all references to the first dose of LCM in this SAP refer to the first dose of LCM during SP848 (ie, not the first dose of LCM from the previous study in which study

participants participated prior to SP848 for long-term follow-up study participants). Unless otherwise noted, all references to the last dose of LCM in this SAP refer to the last dose of LCM in the study.

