#### 8.4.2 Electrocardiograms (ECGs)

Standard 12-lead ECGs (2 interpretable recordings [20 to 30 minutes apart]) will be performed throughout the study, according to the tabular schedule of study procedures.

For ECGs, Baseline will be defined as the average of all pre-dose interpretable readings. Assessments with missing time on day of first dose will be assumed pre-dose. For all post-Baseline visits, the average of all interpretable readings at the specified visit will be used for summaries.

Observed values of ECG results will be summarized for each visit and Last Visit. Change from Baseline in ECG results will be summarized for all post-Baseline visits, and Last Visit. This will be summarized overall and repeated by weight band using the levels defined in Section 3.2.10.

The number and percentage of study participants with no abnormality, an abnormal but not clinically significant finding, and a clinically significant finding, will be summarized for all visits, and Last Visit. Percentages will be relative to the number of study participants with an

ECG assessment at each visit. Study participants are counted at most once at each visit based on the worst observed outcome across all abnormalities reported at that visit.

Summaries of shifts from Baseline to post-Baseline visits, and from Baseline to Last Visit will also be provided based on the categories normal, abnormal, not clinically significant, and abnormal, clinically significant.

A listing of ECG data will be provided for all study participants with other significant TEAEs in the Cardiac and ECG Related Terms category defined in Appendix 12.2. A subject data listing of all ECG parameter values for all study participants will also be presented. Listings will include results from each recording and the average of all recordings.

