### 10.1 Seizure counts

At Screening of SP847 (or other LCM pediatric clinical studies in epilepsy) or at the Screening Visit of SP848 (for study participants who directly enrolled into SP848) study participants/caregivers (including parents/legal guardians) will be asked how many seizures the subject has had in the previous 4 weeks; this will serve as a historical Baseline. After the subject is enrolled in the SP848 study, seizure data will be collected in diaries provided to study participants/caregivers (including parents/legal guardians). Each subject/caregiver (including parent/legal guardian) will keep a diary to note daily seizure activity throughout the current study. The subject/caregiver (including parent/legal guardian) should be reminded to bring the diary with them at each clinic visit. The following information will be recorded:

- Seizure type
- Seizure frequency

Each seizure code in the clinical database will be mapped to exactly 1 of the ILAE seizure codes based on the 1981 ILAE classification (Seizure Count CRF/eCRF module).

Determination of Baseline Period seizures will be made utilizing both the historical Baseline and the seizure diary data collected from the date of the Screening Visit to the day prior to the date of first dose of LCM.

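### Prescription-lacosamide (RxL) participants from EP0060 get an on-drug Baseline for everything except questionnaires, and the ECG Baseline does not say which study's first dose it precedes

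*SAP*

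**What the plan says.** **General rule.** SAP 3.3 takes each participant's "last non-missing value collected prior to the first dose of LCM in the original study for rollover subjects and in SP848 for direct enrollers" as Baseline, and this yields "unless otherwise noted for a specific type of data".

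**EP0060 rule.** The same section says that "the baselines for the questionnaires will consider each EP0060 enrollment group separately". It describes RxL participants as already taking commercially supplied oral lacosamide and concludes that "for RxL group there will be no baseline data as they were on oral LCM prior to EP0060".

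**Seizures.** Under 10.1, at Screening of the previous study (or of SP848 for direct enrollers) the family "will be asked how many seizures the subject has had in the previous 4 weeks; this will serve as a historical Baseline".

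**ECG.** Section 8.4.2 has its own definition: "For ECGs, Baseline will be defined as the average of all pre-dose interpretable readings". It adds that readings with no time on the day of first dose count as pre-dose. It names no study in either place.

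**Meaning of first dose.** Section 3.2.1.1 states that, unless otherwise noted, "all references to the first dose of LCM in this SAP refer to the first dose of LCM during SP848".

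**The concern.** The reason the SAP gives for denying RxL participants a questionnaire Baseline, that they were already on the drug, applies equally to every other variable, yet the rule stops at questionnaires. No section excludes or marks these participants elsewhere. The Safety Set (3.5.1) needs one dose and the Full Analysis Set (3.5.3) needs one completed post-Baseline diary, so RxL participants enter both.

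Their on-drug reference values then feed:
- percent change and responder status (10.1.2 to 10.1.4);
- laboratory change and TEMA, which requires a normal Baseline (8.3);
- vital-sign change, and the criteria at 17 years and over that use change from Baseline (8.4.1);
- ECG change, shift and treatment-emergent tables (8.4.2).

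The ECG definition raises a second question, for all rollovers. They enter SP848 on the lacosamide dose from the previous study (2.4.1.1). If pre-dose means before the first SP848 dose, parent-study ECGs recorded on lacosamide belong in the average. Two programmers could derive different Baselines from the same text. On-drug readings in the average shrink the measured change, raise the level needed to meet a relative criterion, and can remove the treatment-emergent flag from someone already abnormal on drug.

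**Working it through.** The SAP gives no figure to reproduce here, because all summaries are descriptive (3.1). The check compares the texts and then bounds the size.

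**1. What Baseline an RxL participant receives**

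| Data | Governing text | State at Baseline |
|---|---|---|
| Questionnaires | 3.3, EP0060 paragraph | No Baseline |
| Laboratory, vital signs | 3.3, general rule; original study is EP0060 | On prescribed lacosamide |
| ECG | 8.4.2, under either anchor | On prescribed lacosamide |
| Seizure count | 10.1, 4 weeks before parent-study Screening | On prescribed lacosamide, if a count was collected (length of prior use not given) |

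**2. How many participants (2.5)**

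- EP0060 cap: 100 of about 400, or 25%. The RxL share is not stated. At an assumed 10%, 25% or 50% of EP0060 it is 10, 25 or 50 participants, or 2.5%, 6.25% or 12.5% of 400.
- Direct enrollers at their caps: 100 + 46 + 60 = 206. Rollovers: 400 − 206 = 194, or 48.5%.

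**3. Seizure effect**

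If lacosamide had already cut frequency by a fraction c before the Baseline count, that cut shows as 0% change. A participant then needs a total reduction of 1 − 0.5(1 − c) from the off-drug level to count as a 50% responder. For assumed c of 25%, 50% and 75% this is 62.5%, 75% and 87.5%.

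The shift in a pooled responder rate is r × (p0 − pR), where r is the RxL share, p0 the response rate with a drug-free Baseline and pR the rate in RxL. The rates are assumptions:

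| RxL share r | p0 − pR = 20 points | p0 − pR = 40 points (e.g. 50% against 10%) |
|---|---|---|
| 2.5% | 0.5 points | 1 point (50% becomes 49%) |
| 6.25% | 1.25 points | 2.5 points (47.5%) |
| 12.5% | 2.5 points | 5 points (45%) |

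The tables concerned cover participants with partial-onset seizures and a usable Baseline, so r in those tables may differ from the share of 400.

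**4. ECG anchor for other rollovers**

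- For the SP848 anchor: 8.4.2 refers to the first dose without qualification, 3.2.1.1 makes that the SP848 dose, and 3.3 lets a type-specific definition override.
- For the original-study anchor: 3.3 sets it for safety variables in general, and 8.4.2 may change only the last value to an average.

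Under the SP848 anchor, with one drug-free visit and k on-drug visits weighted equally and a constant drug effect, the hidden fraction is k/(k+1): 50% for k = 1 and 75% for k = 3. The SAP does not give k.

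An example with assumed values: off-drug PR 140 ms, drug shift 10 ms, SD of change 10 ms.

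| Baseline | Mean change seen | PR needed for a 25% increase |
|---|---|---|
| Drug-free | 10 ms | 1.25 × 140 = 175 ms |
| Equal mix | 5 ms | 1.25 × 145 = 181.25 ms |
| On-drug | 0 ms | 1.25 × 150 = 187.5 ms |

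The chance of flagging falls from 1 − Φ(2.5) = 0.6% with a drug-free Baseline to 1 − Φ(3.75) = 0.01% with a fully on-drug one.

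**The case against.** **The ECG rule may already be right.** Section 3.3 fixes the original-study anchor for safety variables, and 3.2.1.1 itself yields where the plan notes otherwise. The Amendment 4 log (13.4, Change #11) says the first-dose date for rollovers and direct enrollers was clarified in 3.3, which suggests the original-study anchor was intended. A reader might infer that rollover ECG Baselines are definitely on-drug, but the documents do not support that. What stands is that 8.4.2 was not aligned: the logged Amendment 4 change to it (Change #24) concerns age only.

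**The seizure effect may be smaller or absent.** EP0060 is an intravenous trial of about 1 to 5 days (4.2.7), and the SAP does not show whether it collects a historical seizure count. Without one, percent change cannot be computed and RxL participants drop out of those tables. This limits the size. It does not remove the need for a rule.

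**Large effects are not supported.** With the assumed 50% and 10% response rates, a 25% RxL share would lower pooled response to 40%. That needs every EP0060 participant to be RxL and all 100 places to be filled, whereas 3.3 names three enrolment groups.

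**Safety signals are not lost.** The primary safety variables (2.3.1) are TEAEs, SAEs and withdrawals due to TEAEs. TEAEs are dated from the first SP848 dose (8.2), so they do not depend on this Baseline. ECG observed values are tabulated by visit, clinically significant findings are summarised, all values are listed, and many ECG criteria are absolute. A reader might infer that ECG prolongation would be missed altogether. That goes too far: change and treatment-emergent tables would be weakened, not the whole record.

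**Dropping RxL participants from safety tables would do harm.** A participant with normal values at EP0060 entry who becomes abnormal in SP848 would vanish from the treatment-emergent tables. It would also conflict with 3.5.1, which puts all safety analyses on the Safety Set. This objection stands in full and shapes the fix.

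**Conclusion.** The RxL point holds on the text. The SAP recognises that these participants have no drug-free Baseline, acts on it for questionnaires only, and pools their on-drug reference values unmarked everywhere else. The bias is toward no change. Its size is unknown because the RxL share is not given. Under the assumed shares and response gaps it is about 0.5 to 5 percentage points in pooled response, and only if EP0060 supplies a seizure count.

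The ECG point holds as a conflict between 8.4.2 with 3.2.1.1 and the rule in 3.3, not as a proven error. Up to about 194 of 400 participants could be affected. RxL ECG Baselines are on-drug whichever anchor is used, so the ambiguity matters for the remaining rollovers. The dilution depends on how many on-drug readings enter the average, which the SAP does not give.

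The study is descriptive and its primary safety variables are untouched. Both points should be corrected before the tables are programmed, but neither undermines the study's main output.

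**What to change.** **Section 3.3, seizures.** Extend the RxL no-Baseline rule to seizure change, percent-change and responder summaries, and keep RxL participants in the summaries of observed values.

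**Section 3.3, safety.** For laboratory, vital-sign and ECG change, shift and treatment-emergent tables, keep RxL participants in the Safety Set. Show them separately, or footnote that their reference value was taken on lacosamide.

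**Section 8.4.2.** State that ECG Baseline is the average of all interpretable readings before the first lacosamide dose in the original study for rollovers, or in SP848 for direct enrollers. The sentence on missing times should refer to the same dose.

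**Cost.** A few sentences, a slightly smaller n in the seizure change tables and one extra display or footnote. No new data are needed.

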### **3.4 Protocol deviations**

Important protocol deviations are deviations from the protocol which could potentially have a meaningful impact on either the primary or secondary outcomes for an individual study participant. The criteria for identifying important protocol deviations and the classification of

important protocol deviations will be defined separately in the Specification of Protocol Deviations (SPD) document. To the extent feasible, rules for identifying protocol deviations will be pre-defined without review of the data and without consideration of the frequency of occurrence of such deviations. Whenever possible, criteria for identifying important protocol deviations will be implemented algorithmically to ensure consistency in the classification of important protocol deviations across all study participants.

In general, protocol deviations will be considered according to the following general categories:

- Inclusion criteria
- Exclusion criteria
- Withdrawal criteria
- Prohibited concomitant medications
- LCM dosing regimen
- Procedural non-compliance

Important protocol deviations will be reviewed as part of the Data Review Meeting (DRM) prior to database lock. A list of study participants with important protocol deviations will be agreed upon during the DRM and will be documented in the DRM minutes.

In addition, protocol deviations related to the impact of the global pandemic of coronavirus disease 2019 (COVID-19) will be documented.

### **3.5 Analysis sets**

#### **3.5.1 Safety Set**

The Safety Set (SS) will consist of all enrolled study participants who took at least 1 dose of LCM in this study. All safety analyses will be performed on the SS.

#### **3.5.2 Pharmacokinetic Per-Protocol Set**

The Pharmacokinetic Per-Protocol Set (PK-PPS) will consist of all study participants from the SS having provided at least 1 measurable post-dose plasma sample (with recorded sampling time) on at least 1 visit with documented LCM intake times.

#### **3.5.3 Full Analysis Set**

The Full Analysis Set (FAS) will be used for the analysis of seizure data and will consist of all study participants in the SS, who have at least 1 completed post-Baseline seizure diary.

### **3.6 Treatment assignment and treatment groups**

This is an open-label study; study participants will not be randomized.

Where specified within this SAP, data will either be summarized by age group overall across all LCM doses or by modal daily LCM dose (defined in Section 3.2.8).

### **3.7 Center pooling strategy**

No pooling of centers is planned for this study.

### **3.8 Coding dictionaries**

Medical history and AEs will be coded using the Medical Dictionary for Regulatory Activities (MedDRA® v16.1). Medications will be coded using the World Health Organization Drug Dictionary (WHODD 3Q13). Medical procedures will not be coded.

### **3.9 Changes to protocol-defined analyses**

#### **3.9.1 Handling of dropouts or missing data**

The following protocol-defined method of analysis is no longer applicable for this study:

- All data will be used to their maximum possible extent, but without any imputations for missing data for any parameter. Study participants who discontinue from the study prematurely will be evaluated based on the data collected at each visit attended.

This will be replaced with the following method of analysis (see Section 4.2):

- No imputation of missing values for analysis parameters is planned unless otherwise noted. Imputations for missing or partial values for dates for AEs and concomitant medications will be applied to determine if an event is to be considered treatment-emergent or concomitant. Across safety and efficacy analysis, only reported data will be used in each analysis time interval.

#### **3.9.2 Examination of subgroups**

A subgroup for weight which was not protocol-defined has been included in Section 3.2.

## **4 STATISTICAL/ANALYTICAL ISSUES**

### **4.1 Adjustments for covariates**

No statistical testing is planned; therefore, this section is not applicable for this study.

### **4.2 Handling of dropouts or missing data**

#### **4.2.1 Missing data**

No imputation of missing values for analysis parameters is planned unless otherwise noted. Imputations for missing or partial values for dates for AEs and concomitant medications will be applied to determine if an event is to be considered treatment-emergent or concomitant. Across safety and efficacy analysis, only reported data will be used in each analysis time interval.

With respect to AEs, events with missing intensity will be assumed to be severe. Events with missing relationship to LCM per the investigator will be assumed to be related. Incomplete or missing dates for events will be handled as described in Section 4.2.2.

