#### **4.2.2 Incomplete dates for adverse events and concomitant medications**

For analyses of AEs and concomitant medication usage, a complete date must be established in order to correctly identify the AE or medication as occurring during treatment or not. For purposes of imputing missing components of partially-reported start and stop dates for AEs and for medication use, the algorithms listed below will be followed. Start and stop dates of AEs or concomitant medication will be displayed as reported in the subject data listings (ie, no imputed values will be displayed in data listings).

- Missing start day, but month and year present:  
If the start of LCM occurred in the same month and year as the occurrence of the AE/concomitant medication, the start day of the event/concomitant medication will be assigned to the day of first intake of LCM. Otherwise the start day will be set to the 1st day of the month.
- Missing start day and month, but year present:  
If the start of LCM occurred in the same year as the occurrence of the AE/concomitant medication, the start day and month will be assigned to the date of first intake of LCM. Otherwise the start day and month will be set to January 1st.
- Missing end day, but month and year present:  
The end day will be set to the last day of the month.
- Missing end day and month, but year present:  
The end day and month will be set to the maximum of the date of study termination or the date equivalent to 30 days after last intake of LCM.

However, if the study termination year and year for the date which is 30 days after last intake of LCM are greater than the event/concomitant medication year, the day and month are to be set to December 31st.

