#### **4.2.3 Definition of concomitant medication in case of missing dates**

With respect to definition of medication as concomitant, the following rule will be applied in case of completely missing stop and/or start date information:

Medications with a missing start date whose stop date is either unknown or after the date of the first dose of LCM will be considered as concomitant medication. Medications with missing start date whose stop date is prior to first intake of LCM will not be considered concomitant.

In subject data listings, dates will be displayed as reported.

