#### **4.2.6 General imputation rule for incomplete dates**

Where necessary for the calculation of derived variables, partial dates will be completed using the earliest calendar date based on the partial date provided. This rule is valid for all partial dates with the exception of the following:

- Start and stop dates of AEs
- Start and stop dates of concomitant medication
- Start and stop dates of LCM
- Start and stop dates of seizure diary data

Completely missing dates will not be replaced and the corresponding derived variables will be set to missing.

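### The SAP promises imputation for missing adverse event dates but gives no rule when the onset date is completely missing, so treatment-emergent status for such events is contradictory or undefined

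*SAP*

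**What the plan says.** SAP 4.2.1 makes two commitments. The first is general: "Imputations for missing or partial values for dates for AEs and concomitant medications will be applied", the purpose being to settle treatment-emergent or concomitant status. Section 3.9.1 repeats this as a formal replacement for the protocol's method. The second is a pointer specific to AEs: "Incomplete or missing dates for events will be handled as described in Section 4.2.2".

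Section 4.2.2 explains why a date is needed: "a complete date must be established in order to correctly identify the AE or medication as occurring during treatment or not". It then limits its scope: "For purposes of imputing missing components of partially-reported start and stop dates for AEs". Its most incomplete start-date case is "Missing start day and month, but year present".

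Completely missing dates are treated as a separate case elsewhere. Section 4.2.3 does so for medications ("With respect to definition of medication as concomitant, the following rule will be applied in case of completely missing stop and/or start date information"), and 4.2.4 does so for the last LCM administration. Neither covers AEs.

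Section 4.2.6 gives an earliest-date rule for partial dates and lists AE start and stop dates among the exceptions to it. After that list comes a further sentence: "Completely missing dates will not be replaced and the corresponding derived variables will be set to missing".

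Section 8.2 classes AEs as pre-treatment, treatment-emergent or post-treatment by onset relative to SP848 dosing. An intensity that worsens on or after first dose also makes an event treatment-emergent. No default class is given for an event that cannot be placed.

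**The concern.** The pointer from 4.2.1 leads to a section that does not contain the promised rule. The one sentence that could fill the gap, at the end of 4.2.6, points the other way, because it leaves the derived status missing instead of imputing it.

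Two of the three primary safety variables in 2.3.1, TEAE incidence and withdrawal from the study due to TEAEs, are restricted to treatment-emergent events. So are the serious-TEAE, other-significant-TEAE and PDILI tables and the titration-period and time-interval tables in 8.2. An AE whose flag is missing is absent from all of them.

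This also runs against the SAP's own approach. Under 4.2.1, missing intensity is taken as severe and missing relationship as related. Under 4.2.3, an undated medication counts as concomitant unless it stopped before LCM. An undated AE has no such protection.

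**Working it through.** No figure in the SAP can be reproduced here. The check is a trace of one AE, with day, month and year of onset all missing, through each section that could decide its status.

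1. **4.2.1.** Promises imputation for missing as well as partial AE dates and refers to 4.2.2.
2. **4.2.2.** One start-date rule needs month and year; the other needs the year. With the year absent, neither applies. The end-date rules do not supply an onset.
3. **4.2.3.** Has the right shape, since it uses the stop date when the start date is unknown ("Medications with a missing start date whose stop date is either unknown or after the date of the first dose of LCM"), but it is confined to medications.
4. **4.2.4.** Concerns the last LCM dose only.
5. **4.2.6.** Two readings are possible.
   - *Literal.* The exception list qualifies the partial-date rule. The sentence on completely missing dates stands after the list and is unqualified, so it reaches AE dates. The flag is then missing, contrary to step 1.
   - *Exception.* The list removes AE dates from 4.2.6 altogether. No rule then exists anywhere in the SAP.
6. **8.2.** Under both readings onset gives no class. Only a dated worsening on or after the first SP848 dose could make the event a TEAE.

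Dependence of the primary safety variables (2.3.1) on the flag:

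- TEAE incidence: depends on it.
- SAE incidence: does not. Section 8.2 tabulates serious AEs separately from serious TEAEs.
- Withdrawal due to TEAEs: depends on it.

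Two of three are exposed. The tables by period and by time interval need an onset date as well as a flag, so even a programmer who sets the flag to yes cannot place the event without an imputed date.

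**Scale (illustration only).** The SAP does not say how many AEs lack any onset date. Assume a Safety Set of N = 400, the approximate ceiling in 2.5. If k participants have an undated event as their only TEAE, incidence falls by 100 × k / N percentage points:

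- k = 1: 100 × 1/400 = 0.25
- k = 5: 100 × 5/400 = 1.25
- k = 10: 100 × 10/400 = 2.5

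For incidence of any TEAE, k should be near zero, because a participant with another dated TEAE is still counted. For a rare preferred term, such as those in Table 12–3, one lost event changes the reported count.

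**The case against.** The strongest reply is that the stated intent is to impute. Section 4.2.1 says so, 3.9.1 repeats it, and AE dates are on the 4.2.6 exception list. On that view there is no plan to exclude anything, only an unfinished cross-reference. This stands in part. The exception reading is tenable, and under it the direction of any error depends on a programming default, so one cannot say that events are only ever removed. That one-way loss follows only if the flag is left missing. The reply does not supply a rule, however. Under both readings the promised imputation is absent.

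A reader might go further and infer that undated AEs fall out of the primary safety counts as a whole. The SAP does not support that. SAE incidence is not conditional on treatment emergence, 8.2 lists every reported AE, and a dated worsening can still qualify an event.

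It is also fair to say that the effect is likely to be minor. The gap concerns only onset dates lacking even the year, which should be rare after data cleaning, and all summaries are descriptive. That limits the size of the problem. But the authors thought the same case worth a rule for concomitant medication.

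Finally, setting undated onsets to the first SP848 dose has a price. It places those events in the Titration Period for direct enrollers and in the ≤3-month interval. For rollover participants that date is not the first LCM exposure (3.2.1.1), so an event carried over from the parent study could be counted as new. This objection stands and is the reason to footnote such events.

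**Conclusion.** The gap is real and worth closing. For an AE with a completely missing onset date, the SAP either contradicts its own commitment to impute (literal reading of 4.2.6) or says nothing (exception reading). Unless they have a dated worsening on or after first dose, such events could be lost from two of the three primary safety variables and from the TEAE-based tables.

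The expected numerical effect is small, but this rests on an assumption that such dates are rare, since the SAP gives no number. The 0.25-point figure per participant rests on an assumed Safety Set of 400 and on the undated event being that participant's only TEAE. The main reason to act is that a derivation feeding primary variables should not be settled by a programming default after the data are in view.

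**What to change.** Two additions to the SAP:

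1. In 4.2.2: an AE whose start date is completely missing is treatment-emergent, with onset set to the date of the first SP848 LCM dose, unless its reported or imputed end date is before that dose, in which case it is pre-treatment.
2. In 4.2.6: the last sentence does not apply to AE dates.

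This follows conventions already in the SAP. Section 4.2.2 assigns the first-intake date when a partial onset falls in the same month or year as the start of LCM, and 4.2.3 uses the stop date in the same way for medications. The existing end-date rules work with it unchanged. For example, an end date known only by a year before that of first dose becomes 31 December of that year, and the event is pre-treatment.

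The cost is a short text change and slightly higher TEAE counts, concentrated in the Titration Period and the ≤3-month interval, possibly with some parent-study events in rollover participants. Mark these events with a footnote in the affected tables so that a reader can see how many rest on an imputed onset.
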